## 6. Safety Reporting

All subjects will be assessed regularly for potential adverse events (AEs) occurring at any time after the subject signs the informed consent, until discharge after the last dose of study medication. AEs ongoing at the time of last dose of study medication will be followed until resolution or until 30 days after the last dose of study medication, whichever comes first. Post-study follow-up will be by telephone or e-mail after subjects are discharged. All subjects dosed will be contacted per the schedule above and queried regarding the occurrence of AEs and serious adverse events (SAEs).

### 6.1 Terminology

An *Adverse Event (AE)* is defined as any untoward medical occurrence associated with the use of a drug in humans, whether or not considered drug related. An AE (may also be referred to as an adverse experience) can therefore be any unfavorable and unintended sign (including an abnormal laboratory finding, for example), symptom, or disease temporally associated with the use of a medicinal (investigational or marketed) product, whether or not considered related to the medicinal (investigational or marketed) product and from any route of administration, formulation, or dose, including an overdose.

A *Serious Adverse Event (SAE)* is any untoward medical occurrence that at any dose results in any of the following outcomes:

death;

is a life-threatening adverse event (defined as an event in which the subject was at risk of death at the time of the event; it does not refer to an event that hypothetically might have caused death if it were more severe);

requires in-patient hospitalization or causes prolongation of existing hospitalization;

a persistent or significant disability/incapacity or substantial disruption of the ability to conduct normal life functions;

a congenital anomaly/birth defect;

is an important medical event. This is defined as a medical event that may not be immediately life-threatening or result in death or hospitalization but, based upon appropriate medical and scientific judgment, may jeopardize the subject and may require medical or surgical intervention to prevent one of the other serious outcomes listed in the definition above. Examples of such events include, but are not limited to, intensive treatment in an emergency room or at home for allergic bronchospasm; blood dyscrasias or convulsions that do not result in hospitalization.

If either the sponsor or investigator believes that the event is serious, the event must be considered serious and be evaluated by the Sponsor for expedited reporting.

Admission for gastroenteritis is not a serious adverse event, as the gastroenteritis is a preexisting condition, not an adverse event. Admission for gastroenteritis will be considered lack of efficacy, and is recorded as such as a secondary efficacy outcome.

If, however, a patient develops new symptoms in the ED, such as findings leading to a diagnosis of an acute abdomen, and is admitted, that would be considered a serious adverse event.

A *suspected adverse reaction* means any adverse event for which there is a reasonable possibility that the drug caused the adverse event.

An adverse event or suspected adverse reaction is considered *unexpected* if it is not listed in the Investigator's Brochure or is not listed at the specificity or severity that has been observed.

## 6.2 Assessment of Causal Relationship

The following categories and definitions for assessing the causal relationship of an event to the investigational product(s) are provided as a guide to be used for evaluating adverse events reported in this study to determine "suspected adverse reactions" that require expedited reported to regulatory agencies if they are unexpected. In addition to the assessment below, the aggregate number of occurrences will be considered to decide whether the event is a reportable event and requires an IND safety report.

**Table 1. Relationship of Study Medication to Adverse Events**

Unrelated	
The study drug almost certainly (or certainly) did not cause the event. Guidelines:
 
There is no reasonable temporal relationship of the event to the administration of drug;
 
The pattern is inconsistent with that known for the drug; and/or
 
There is another obvious etiology.

Probably not related	
It is more likely that the event is due to another etiology than due to the study drug. Guidelines:
 
There is no reasonable temporal relationship of the event to the administration of drug;
 
The pattern is inconsistent with that known for the drug; and/or
 
There is another more likely etiology.

Possibly related	
It is approximately equally likely that the event is due to the study drug as it is due to another etiology. Guidelines:
 
There is a reasonable temporal relationship of the event to the study drug;
 
The drug seems as likely as other etiologies to have caused the effect

Probably related	
It is more likely that the event is due to the study drug than due to another etiology. Guidelines:
 
There is a reasonable temporal relationship of the event to the study drug;
 
The event may be consistent with a known pattern of drug (or drug class) effects;
 
The drug seems more likely than other etiologies to cause the effect;
 
The adverse event diminished upon cessation of study drug exposure or reduction in dose; and/or
 
The adverse event worsened or recurred upon unintentional re-exposure to the study drug (Intentional rechallenge for the purpose of assigning causality should not be performed.)

Definitely related	The evidence is compelling that the study drug caused the adverse event. Guidelines: There is a reasonable temporal relationship of the event to the study drug; The event is consistent with a known pattern of drug (or drug class) effects; The drug is far more likely than other etiologies to have caused the effect; The adverse event diminished upon cessation of study drug exposure or reduction in dose; The adverse event worsened or recurred upon unintentional re-exposure to the study drug (Intentional rechallenge for the purpose of assigning causality should not be performed.)
Unknown	The data are inadequate to assign any of the above causal relationship categories to the study drug.

### 6.3 Adverse Event Grading and Coding

Adverse events will be graded according to the NCI-CTCAE v 4. These criteria can be accessed at: <http://evs.nci.nih.gov/ftp1/CTCAE/About.html>

For AEs not included in the NCI-CTCAE v 4, the following criteria will apply:

Grade	Description
1	Mild
2	Moderate
3	Severe
4	Life-threatening or disabling
5	Fatal

AEs will be coded, grouped and tabulated by MedDRA preferred terms by body system organ class. MedDRA version 13.1 will be used for the entire study.

### 6.4 Handling of Serious Adverse Events

Adverse events classified as serious must be recorded on the AE page of the CRF and require expeditious handling and reporting to the sponsor, RedHill Biopharma, to comply with regulatory requirements. These SAEs will include deaths, regardless of their causal relationship to investigational product. All SAEs must be reported using the Serious Adverse Event Report form. To the extent possible, the descriptive terminologies and other SAE attributes entered on the SAE report form should approximate similar information in the CRF. The completed SAE report form with supporting documentation must be provided to the sponsor within 24 hours of the study site personnel's initial notification/awareness of the event. All telephone communication regarding SAE must be followed by a written report.

Collection of complete information concerning SAEs is extremely important. Thus, follow-up information that becomes available as the SAE evolves, as well as supporting documentation (e.g. hospital discharge summaries, additional lab and test results, autopsy reports, etc.), should be collected subsequently, if not available at the time of the initial report, and immediately sent to sponsor using the same procedure as the initial SAE report. Information on the SAE must be in

sufficient detail to allow for a complete medical assessment of the case and independent determination of causality.

For ease of analysis, worldwide standardization, and regulatory reporting, the sponsor will code each reported adverse event or symptom to its corresponding preferred term and body system/organ class in the MedDRA dictionary version adopted for the study. The principal investigator will be responsible for assessing severity based on the intensity of the event as it presented using the criteria listed in section 6.3, above.

**All SAE reports must be e-mailed or faxed directly to [REDACTED]**

[REDACTED]

[REDACTED]

[REDACTED]

As required, all investigators will be notified of all AE reports that are determined to be serious, unexpected, and related (by the reporting investigator or sponsor) to the investigational product. The notification will be in the form of a Safety Update (Dear Doctor Letter).

The notification is considered an addendum to the current Investigator's Brochure; therefore, upon receiving such notices, the investigator must review and immediately submit a copy to the IRB according to local regulations. The notification must be retained within the Investigator's Brochure. The investigator and IRB will determine if the informed consent requires revision.

## 6.5 Laboratory Test Abnormalities

If any laboratory tests are performed on study, all new abnormal laboratory findings after initial administration of study medication and those abnormal at baseline which change significantly (i.e., by at least one toxicity grade as defined in the National Cancer Institute Common Terminology Criteria for Adverse Events [NCI CTCAE] v4.0) are considered AEs. Laboratory AEs for which there is no clinical intervention will be recorded only on the laboratory data pages of the eCRF. Laboratory AEs not listed in the NCI CTCAE v4.0 will be considered as grade 1 (mild) if there is no clinical effect or intervention. Laboratory values outside the normal range for certain parameters will not be considered AEs if they are generally not considered as indicating an abnormality; this includes such parameters as liver enzymes which are below the normal range. If there is a clinical sequela or intervention, the laboratory abnormality is to be graded according to the criteria used for clinical AEs, described above.

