Patients will be contacted at least once daily for 4 days after discharge from the emergency department to question them about the presence of gastroenteritis symptoms and adverse events, to ask if and when they took study medication, and to ask whether they have returned to normal daily activities. The information recorded by the patient on his/her diary card will form the basis for data collected in the follow-up calls. If during the follow-up period, symptoms progress or worsen or new symptoms develop, the patient may be asked to return for further evaluation. If by day four after discharge (i.e., the day after the last dose of study medication), the patient still notes gastroenteritis symptoms, he or she will be instructed to return to see the investigator or his/her designate for further assessment. In addition, if the investigator is concerned that a patient may not be entering the data promptly and appropriately or as an added stimulus to data entry by the patient, the investigator may also contact the patient.

For patients returning due to persistent gastroenteritis 3 days after discharge from the ED, an interim history and physical examination will be performed. Laboratory studies may be performed if clinically indicated, and results of these studies will be entered into the CRF.

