### 7.5.1 Adverse Events

The NCI-CTCAE v4.0 system will be used to grade new or worsening laboratory abnormalities. New laboratory abnormalities for which there are no CTCAE v4.0 criteria will be assigned grade 1 if there were no clinical effects or interventions, and according to the criteria in section 6.3 if there were clinical effects and/or interventions. AEs will be grouped and tabulated by MedDRA preferred terms by system organ class.

The Medical Dictionary for Regulated Activities (MedDRA) version 13.1 will be used to classify all AEs with respect to system organ class and preferred term.

Summary tables of AEs and SAEs will be prepared by system organ class, preferred term and severity for each treatment group. AEs that lead to premature discontinuation from the study or to death will be listed separately via data listings.

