9. STATISTICAL METHODOLOGY AND STATISTICAL ANALYSES

9.1. Study Population and Demographics

Demographic and pretreatment patient characteristics, including disease parameters and comorbidities, will be summarized with descriptive statistics. The descriptive statistics will include sample size, mean, standard deviation, median, minimum, and maximum for continuous variables and number and percentages for discrete variables.

Baseline chemistry, CBC and urinalyses were performed on selected patients prior to amendment 4. Beginning with amendment 4, instituted in March, 2016, all patients were required to have chemistry and CBC performed; urinalysis remained optional. In addition beginning with amendment 4, pre- and 4 hr post-treatment ECGs were required of all patients.

Data for chemistry, CBC and urinalysis parameters are analyzed by treatment group, as described above. ECGs, which are performed pre- and post-treatment, are analyzed in greater detail, as described below.

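### Protocol 6.5 counts a one-grade laboratory change as an adverse event without saying in which direction, and the by-arm tables will not show how many patients were retested

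*Protocol*

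**What the plan says.** **What counts as a laboratory adverse event.** Protocol 6.5 covers two kinds of finding. The first is "If any laboratory tests are performed on study, all new abnormal laboratory findings after initial administration of study medication". The second is "those abnormal at baseline which change significantly (i.e., by at least one toxicity grade" under NCI-CTCAE v4.0. It then says: "Laboratory AEs for which there is no clinical intervention will be recorded only on the laboratory data pages of the eCRF". Findings with a clinical sequela or intervention are graded like clinical adverse events.

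**What the other sections say.** Protocol 6.1 describes an adverse event as "any unfavorable and unintended sign (including an abnormal laboratory finding, for example"). Protocol 7.5.1 states: "The NCI-CTCAE v4.0 system will be used to grade new or worsening laboratory abnormalities". SAP 9.4 repeats that sentence.

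**When laboratory tests are done.** The study assessments table with its notes, and protocol 5.2.1, place chemistry and CBC at baseline. The emergency department observation list in 5.2.2 has no laboratory test. For patients who return with persistent illness, 5.2.3 says: "Laboratory studies may be performed if clinically indicated, and results of these studies will be entered into the CRF". Baseline data are themselves incomplete. SAP 9.1 reports: "Baseline chemistry, CBC and urinalyses were performed on selected patients prior to amendment 4".

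**What is tabulated.** SAP 7.2 lists laboratory tests as a safety endpoint. SAP 9.4 uses them if they were performed and plans adverse event tables by treatment group. It gives no post-dose laboratory table and no number retested.

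**The concern.** Section 6.5 is the rule a site applies when it decides what to record. Patients enter with acute vomiting, so some baseline values may be deranged and may correct with fluids or replacement. Under an undirected rule, such a correction can be entered as an adverse event. If an intervention was involved, it is not confined to the laboratory pages.

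The second issue is ascertainment. A laboratory abnormality can be found only in a patient who is tested. After dosing, testing depends on the clinical course, and the trial is designed to show that the course differs by arm. If one arm is retested more often, a percentage based on all treated patients mixes the abnormality rate with the testing rate. Should placebo be retested more, RHB-102 would look safer on laboratory events, and a modest laboratory harm could go unseen.

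The third issue is smaller. A patient without a baseline test has no grade from which to judge change, and neither document says how an abnormal later value is then classified.

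**Working it through.** The plan states no figure for laboratory adverse events or for retesting, so there is none to reproduce. The check compares wording first and then does one piece of arithmetic.

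**1. Direction.**

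| Place | Role | Direction |
|---|---|---|
| Protocol 6.1 | defines an adverse event | unfavourable |
| Protocol 6.5 | recording rule, values abnormal at baseline | none stated |
| Protocol 7.5.1 and SAP 9.4 | grading for analysis | new or worsening |

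Section 6.5 is the only one that admits an improvement on its literal wording. Its one-grade rule applies only to values already abnormal at baseline. New findings have a separate rule, and out-of-range values not generally taken to indicate an abnormality are exempt.

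**2. Who can have a laboratory event.** No post-dose test is scheduled. Later values come from return visits (5.2.3) or from usual care in patients still in the emergency department or hospital (5.2.2). The numerator is therefore drawn from retested patients only.

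**3. How far retesting could differ by arm.** Inputs: failure within 24 hours of 40% on placebo and 20% on RHB-102 (protocol 7.1). Assumed, because the documents give nothing: 30–70% of failures retested (f) and 5–30% of successes retested (s).

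- Placebo share retested = 0.4f + 0.6s
- RHB-102 share retested = 0.2f + 0.8s

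| f | s | Placebo | RHB-102 | Ratio |
|---|---|---|---|---|
| 30% | 30% | 0.12 + 0.18 = 30% | 0.06 + 0.24 = 30% | 1.00 |
| 50% | 30% | 0.20 + 0.18 = 38% | 0.10 + 0.24 = 34% | 1.12 |
| 50% | 10% | 0.20 + 0.06 = 26% | 0.10 + 0.08 = 18% | 1.44 |
| 30% | 5% | 0.12 + 0.03 = 15% | 0.06 + 0.04 = 10% | 1.50 |
| 70% | 10% | 0.28 + 0.06 = 34% | 0.14 + 0.08 = 22% | 1.55 |
| 70% | 5% | 0.28 + 0.03 = 31% | 0.14 + 0.04 = 18% | 1.72 |

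With k = f/s the ratio is (0.4k + 0.6)/(0.2k + 0.8), which rises with k. Over the assumed ranges k runs from 30/30 = 1 to 70/5 = 14, so the first and last rows are the limits: 1.00 to 1.72. If failures were retested less often than successes (k below 1), the ratio would be below 1.

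**4. What a ratio of 1.44 would do.** Take the third row and assume 20% of retested patients in each arm have an abnormality.

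- Placebo: 0.26 × 0.20 = 5.2% of 128, about 7 patients
- RHB-102: 0.18 × 0.20 = 3.6% of 192, about 7 patients

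The percentages differ although the rate per patient tested is the same. Conversely, RHB-102 could have 0.20 × 0.26/0.18 = 29% abnormal per patient tested and still show the placebo incidence of 5.2%.

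**The case against.** A reader might infer that the plan systematically scores recovery after rehydration as toxicity. The documents do not support that. An improving value is not unfavourable under 6.1, and both analysis texts grade only new or worsening abnormalities. Laboratory events without intervention stay on the laboratory pages, and nothing says that these enter the adverse event tables. What remains is a recording rule out of line with the rest of the plan. It needs correcting, but it is not the analysis rule.

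A reader might also infer that placebo patients will be retested more often. That is plausible but not established. Protocol 5.2.3 limits follow-up of 24-hour failures after the emergency department to one call at 72–96 hours. The return visit at which tests are mentioned therefore belongs mainly to the daily-contact pathway, which those patients leave. Failures may be retested in the department or hospital, so the net direction is open. The assumed ranges include no difference at all.

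The tables are descriptive, no safety hypothesis is tested, and the counts in the illustration are small. That is fair and limits the weight of the point. A table restricted to retested patients also has a flaw: it conditions on something that happens after randomisation and may depend on treatment. That objection stands, so such a table can describe but cannot serve as a randomised comparison.

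Finally, no text says that an abnormal value without a baseline will be called new. The documents are silent on this.

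**Conclusion.** The point holds in two limited parts. First, the wording of 6.5 conflicts with 6.1, 7.5.1 and SAP 9.4, and a site following it literally could record an improvement as an adverse event. Second, laboratory adverse events can arise only in patients retested for clinical reasons, and the planned output does not show how many those are in each arm. An all-treated incidence is then confounded with testing if retesting differs by arm.

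The size is not known. The ratio of 1.00 to 1.72 rests on the planned failure rates and on assumed retest rates; the incidence figures also rest on an assumed 20% abnormality rate. If the ratio exceeds 1, the distortion favours RHB-102. Severity is minor: this is a matter of safety reporting, and the primary analysis is unaffected.

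**What to change.** **Protocol 6.5.** For values abnormal at baseline, replace the undirected change with the requirement that they *worsen by at least one toxicity grade*. This is a change of a few words and aligns the section with 7.5.1 and SAP 9.4.

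**SAP 9.4.**

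- Keep laboratory adverse events with a clinical sequela or intervention in the adverse event tables, and state whether those held only on the laboratory pages are included.
- Add a descriptive table of baseline-to-post-dose laboratory shifts by arm. Show the number treated, the number retested, and the number with paired values for each test as denominator. SAP 9.4 already follows this principle for paired ECGs.
- List abnormal post-dose values that have no baseline separately, without counting them as new.

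**Cost.** One extra table and one listing, from results already on the laboratory pages. The supplemental SAP records that the study was unblinded on June 3, 2017, so the table should be labelled as added after unblinding. Denominators will be small, and retested patients are a group selected after randomisation; the table should say both.

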## 6.6 Other Safety Considerations

Any clinically significant changes noted during interim or final physical examinations, electrocardiograms, x-rays, and any other potential safety assessments, whether or not these procedures are required by the protocol, should also be recorded on the AE page of the CRF.

## 7. Data Analysis and Statistical Considerations

### 7.1 Sample Size Considerations

The primary endpoint is a composite of the following three parameters from 30 minutes until 24 hours after the first dose of study medication:

- absence of vomiting
- no use of rescue medication, and
- no intravenous hydration

If all of the above three criteria are fulfilled, the patient is considered a treatment success for the primary analysis. If one or more of the above three criteria are not fulfilled, i.e., the patient either experiences vomiting, receives rescue medication or receives intravenous hydration from 30 minutes through 24 hours after the first dose of study medication, the patient is considered a treatment failure.

It is expected that approximately 40% of the placebo group will fail treatment during the 24 hours after initial dosing and that RHB-102 will reduce the incidence of treatment failure by approximately 50%, i.e., to an incidence of 20% in the active treatment group. Patients will be stratified by age (<18,  $\geq$ 18 years of age) and randomized 60:40 to active versus placebo. To demonstrate a statistically significant decrease in the incidence of vomiting with a 2-tailed p-value=0.01 and power=90%, 320 patients will be entered into the study, 192 randomized to RHB-102 and 128 to placebo.

